1.2 SCHEMA

Month -1	Screening

• Total n=56• Obtain informed consent• Screen potential participants by inclusion and exclusion criteria• Obtain history, document concomitant medications, MSA diagnosis and demographics• Assessments: EKG, MoCA, Physical examination and UMSARS, vital signs• Safety assessments: CBC, CMP, CPK, urinalysis and 24-hour urine collection, lipid panel, urine pregnancy test, HIV, hepatitis B and C, QuantiFERON	
Day 1	Randomization and baseline visit

• Sirolimus (n=42)• Placebo (n=14)• Perform randomization• EKG, MoCA, Physical examination and UMSARS, vital signs• Safety assessments: CBC, CMP, CPK, urinalysis and 24-hour urine collection, lipid panel• Collect blood for exosomes• Perform brain MRI (+/- 5 days)• Perform retinal OCT (+/- 5 days)• Administer initial dose of study intervention• Dispense study drug	
Day 8, Day 15, Day 22	Study drug levels

• Measure sirolimus plasma levels (+3 days) and adjust study drug dose accordingly	
Month 1 and Month 2	Safety labs (can be performed locally; adverse event recording performed over the phone)

• CBC, CMP, CPK, urinalysis, and 24-hour urine collection, lipid panel, and plasma sirolimus levels.• Adverse event recording	
Month 3	Follow-up assessments of study endpoints and safety

• Concomitant medications• EKG, physical exam, vital signs, height and weight and UMSARS• CBC, CMP, CPK, urinalysis and 24-hour urine collection, lipid panel, and plasma sirolimus levels.• Adverse event recording• Retrieve study drug• Dispense study drug	
Month 4 and Month 5	Safety labs (can be performed locally; adverse event recording performed over the phone)

• CBC, CMP, CPK, urinalysis and 24-hour urine collection, lipid panel, and plasma sirolimus levels.• Adverse event recording	
Month 6	Follow-up assessments of study endpoints and safety

• EKG, physical exam, vital signs, height and weight and UMSARS• Adverse event recording• CBC, CMP, CPK, urinalysis, and 24-hour urine collection lipid panel, and plasma sirolimus levels.• Obtain blood for exosomes• Retrieve study drug• Dispense study drug	
Month 7 and Month 8	Safety labs (can be performed locally; adverse event recording performed over the phone)

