	a: Albumin, alkaline phosphatase, total bilirubin, bicarbonate, BUN, calcium, chloride, creatinine, glucose, potassium, total protein, AST, ALT, sodium. B: Serum pregnancy test (women of childbearing potential). c: 24-hour urine collection at baseline will be performed only if the baseline visit occurs > 30 days from the 24-hour urine assessment performed as part of the screening visit. d: Sirolimus blood level should be drawn 7 days after previous dose adjustment has taken place. e: If baseline visit (Visit 2) occurs within 15 days of the screening visit, the selected procedures can be foregone and the results of the screening day will be used. S: In-site visit at NYU (denoted in grey) SL: Safety labs visit, this can be done either at NYU or locally. If done locally, a phone call will be performed to inquire about adverse events. Safety labs should be drawn after a light (low fat) breakfast. P: Phone call or video-conference call																		

	Screening (V1) Day -42 to -1
Procedures	Baseline / Random. Visit 2 Day 1
	Study Visit 3 Day 7 +3 day
	Study Visit 4 Day 14 + 3 day
	Study Visit 5 Day 21 +3 day
	Study Visit 6 Day 28 +3 day
	Study Visit 7 Day 56 +15 day
	Study Visit 8 Day 84 +15 day
	Study Visit 9 Day 112 +15 day
	Study Visit 10 Day 140 +15 day
	Study Visit 11 Day 168 +15 day
	Study Visit 12 Day 196 +15 day
	Study Visit 13 Day 224 +15 day
	Study Visit 14 Day 252 +15 day
	Study Visit 15 Day 280 +15 day
	Study Visit 16 Day 308 +15 day
	End of study V17 Day 336 +15 day
	Phone followup V18 Day 350 +/-5 day
	Safety assess. V19 Day 365 +/-5 day
	CPK: Creatine Phosphokinase

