2.3 RISK/BENEFIT ASSESSMENT

2.3.1 KNOWN POTENTIAL RISKS

Specific adverse reactions associated with the administration of sirolimus 2 mg once a day occurred at a significantly higher frequency than in the respective control group. These include hypercholesterolemia, hyperlipemia, hypertension, rash, acne, anemia, arthralgia, diarrhea, hypokalemia, and thrombocytopenia. The elevations of triglycerides and cholesterol and decreases in platelets and hemoglobin occurred in a dose related manner in patients receiving sirolimus (see FDA-approved package insert information (54)). Combination of sirolimus with statins and other medications for dyslipidemia has been shown to increase the risk of rhabdomyolysis. To evaluate the risk of rhabdomyolysis, CPK will be checked at each study visit including safety laboratory assessments, and patients will be specifically asked about new-onset myalgia at each study visit.

Risk involving non-contrast brain magnetic resonance imaging (MRI): There are no known risks or adverse effects resulting directly from exposure to non-contrast MRI. However, subjects who have a pacemaker or metal objects in their body such as shrapnel or metal in the eye should not have the scan performed. Every care will be taken to prevent this, including a thorough interview of each patient and review of his/her medical history to ensure that no metallic implants are present in patient's body.

There is a potential risk of burns in the event that patients are inadvertently carrying metallic ferromagnetic objects or particles in or on the patient. These include but are not limited to pulse 15ximeter, EKG leads, or skin tattoos. Every care will be taken to prevent this, including a thorough screening of each patient to ensure that no metallic materials are present in or on the patient's body. Additionally, the power limit of the brain MRI will be adjusted as necessary. The introduction of metallic ferromagnetic objects in the scanner room may result in magnetic displacement of the metallic object causing injuries to the patient. To reduce this risk, patients and every medical personnel near the MRI magnet will remove metal contents from them.

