Participants will be dispensed study medication during the baseline visit. In case this is not possible, participants will be mailed the study medication within 30 days of the baseline visit.

The case report forms will note the date when the subject will start the study medication.

Participants will also undergo a non-contrast brain MRI with specific sequences to evaluate the diffusion at the putamen and pons. The brain MRI will be performed at the NYU Center for Biomedical Imaging. There will be a brain MRI period of up to 7 days after the baseline visit (i.e., subjects must be scanned within 7 days after the baseline visit).

Scheduled site visits: assessment of the primary outcome measure and safety labs will be conducted on-site at study visits at Visit 8 (month 3 after initiation of study drug), Visit 11 (month 6 after initiation of study drug), Visit 14 (month 9 after initiation of study drug), and Visit 17 (month 12 after initiation of study drug) (+ 15 days). We will accept a visit window of 15 days after the target date. The following tasks will be performed:

- EKG
- Concomitant medications
- Adverse event recording
- Physical exam
- Vital signs
- UMSARS scale
- CBC, CMP, CPK (8 ml of blood) and urinalysis with 24-hour urine collection
- Lipid panel
- Sirolimus levels in blood (5 ml of blood)
- Retrieve study drug
- Dispense study drug. If dispensation of study drug is not possible during the visit, the study drug will be mailed within 15 days.

Safety Laboratory Visits: Assessment of safety will be conducted on-site or locally at study visits 7 days (with a window of 3 days after the target date) after initiation of study drug (Study Visit 3), and 7 days after the patient has increased dose of study drug (i.e., Study Visit 4, Study Visit 5 and Study Visit 6, with

a window of 3 days after the target date) during the first month of study drug treatment. We will accept a visit window of 3 days after the target date of these visits.

Assessment of safety visits will also occur on-site or locally on Month 2 (Study Visit 7, this visit may be skipped in previous visits were delayed, to ensure that Visit 8 occurs at Month 3), Month 4 (Study Visit 9), Month 5 (Study Visit 10), Month 7 (Study Visit 12), Month 8 (Study Visit 13), Month 10 (Study Visit 15), and Month 11 (Study Visit 16). We will accept a visit window of 15 days before or after the target date of these visits.

The following safety laboratory assessments will be performed:

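### Section 4.1 ties Visits 4–6 to a dose increase, but the SoA schedules them for everyone; read literally, 4.1 gives a participant kept at 2 mg one first-month safety panel instead of four

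*Combined protocol and SAP*

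**What the plan says.** **SoA (1.3).** Visits 3 to 6 have fixed days, for example "Study Visit 4 Day 14 + 3 day". CBC, CMP, CPK, lipids, urinalysis and adverse-event review are marked at all four, with no condition on dose. The 24-hour urine collection is blank at these visits and first appears on treatment at Visit 7. Footnote d concerns only the drug level: "Sirolimus blood level should be drawn 7 days after previous dose adjustment has taken place".

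**Section 4.1, Safety Laboratory Visits.** Visit 3 falls 7 days (+3) after drug start. The remaining first-month visits fall "7 days after the patient has increased dose of study drug (i.e., Study Visit 4, Study Visit 5 and Study Visit 6, with" a three-day window). The list then moves to Month 2 (Visit 7). The tests named for these visits include a 24-hour urine.

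**Schema (1.2).** For Days 8, 15 and 22 it names one task: "Measure sirolimus plasma levels (+3 days) and adjust study drug dose accordingly". The entry for Months 1 and 2 begins "Safety labs (can be performed locally; adverse event recording performed over the phone" and lists a full panel with 24-hour urine.

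**Section 8.2.** Laboratory tests are done at every study visit, but the list of interim months starts at Month 2, and the itemised tests are for the monthly assessments from Visit 7 on.

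**Section 6.1.2.** A participant at 5–20 ng/mL on 2 mg keeps that dose until a next level visit with a +3-day window; the visit number is missing from the text.

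**The concern.** The two texts that site staff would use to book first-month visits disagree on whether Visits 4, 5 and 6 happen for someone whose dose is not raised. If 4.1 is followed, extra panels go to participants just moved to a higher dose. None go to those whose level on 2 mg is in range, or is above 20 ng/mL but not above the 30 ng/mL that leads to exclusion.

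What is at stake is early detection of laboratory toxicity. Section 2.3.1 describes dose-related changes in lipids, platelets and hemoglobin. It also commits, because of rhabdomyolysis risk with lipid-lowering drugs, that "CPK will be checked at each study visit including safety laboratory assessments". Statins and fibrates are allowed (6.5). A visit that is never booked cannot meet that commitment. Unscheduled laboratory tests (4.1) and participant calls between visits (8.2) remain available, but both need someone to notice a problem first.

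**Working it through.** **Inputs.** SoA days: Visit 3 = 7, Visit 6 = 28, Visit 7 = 56. Windows: Visits 3–6, +3 days in both texts; Visit 7, +15 days in the SoA ("Study Visit 7 Day 56 +15 day") and 15 days either side in 4.1. Dose steps in 6.1.2: 2 to 4 to 6 mg, so at most two increases during dose selection.

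**First-month safety panels.**
- SoA: Visits 3, 4, 5 and 6 = 4, for everyone.
- Section 4.1 read literally: 1 (Visit 3) + the number of increases. No increase: 1 + 0 = 1. One: 1 + 1 = 2. Two: 1 + 2 = 3.
- Schema, counting only what it names: 1, at Month 1.

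**Panels through Visit 7 (Month 2), no increase.** SoA 4 + 1 = 5; section 4.1 1 + 1 = 2; schema 1 + 1 = 2.

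**Gap before the Visit 7 panel, no increase.**

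| Text followed | Previous panel | Visit 7 | Nominal | Shortest | Longest |
|---|---|---|---|---|---|
| Section 4.1 | Visit 3, Day 7–10 | Day 41–71 | 56 − 7 = 49 | 41 − 10 = 31 | 71 − 7 = 64 |
| SoA | Visit 6, Day 28–31 | Day 56–71 | 56 − 28 = 28 | 56 − 31 = 25 | 71 − 28 = 43 |

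The permission to skip Visit 7 is left out of both rows, because it applies only when earlier visits ran late.

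**How many participants.** The plan gives no expected share staying at 2 mg, so the number on sirolimus could be anywhere from 0 to 42. Up to 14 placebo participants could share the visit pattern through sham dose paths, but they carry no drug risk.

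**The case against.** The best counter-argument is that the one-panel reading does not fit 4.1 itself. Dose selection allows only two increases, so a strict only-after-an-increase rule would trigger Visits 4 and 5 and leave Visit 6 with nothing to trigger it. Yet 4.1 names all three visits together. Read as a timing rule (when the dose has gone up, wait 7 days), the clause makes sense and agrees with footnote d and with 6.1.2. Section 4.4 defines completion by the SoA, and the +3-day next-level visit in 6.1.2 suits a first-month visit. This stands, and it makes the SoA the probable intention. It does not remove the conflict: 4.1 never says that Visits 4–6 take place without an increase, and a coordinator could reasonably apply it as worded.

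A reader might infer that the protocol sets three rival schedules. That goes too far. The schema is an abbreviated summary: its Month 12 entry also omits the EKG, adverse-event recording and drug levels that the SoA marks at Visit 17. Its silence about panels on Days 8, 15 and 22 is weak evidence that none are intended, and it does give a panel at Month 1.

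There are further safeguards. Section 6.1.2 calls for monthly drug levels from drug start once the dose is selected, so a Month 1 blood draw is due; that is not in itself a safety panel, although 4.1 groups the two. The team reviews adverse events weekly (10.1.7), and the PI, medical monitor and independent pharmacist confer monthly (10.1.6). These soften the consequence without supplying the missing laboratory results. It is also fair to say that those affected are on the lowest dose, and nothing in the documents shows that one panel followed by Month 2 would be inadequate for them.

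**Conclusion.** Section 4.1 and the SoA conflict on first-month safety laboratory visits. Under a literal reading of 4.1, a participant not escalated from 2 mg has one first-month panel rather than four and a nominal 49 days (31–64) until the next, against 28 days (25–43) under the SoA. That result rests on two assumptions: 4.1 is applied as worded in preference to the SoA, and the participant has no dose increase in the first month.

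A reader might go further and conclude that participants kept at 2 mg will go unmonitored, that all 56 are exposed to drug risk, or that the trial result is affected. The documents do not support these. Following the SoA removes the gap, and a Month 1 panel as in the schema would shorten it. At most 42 participants receive sirolimus. The laboratory schedule does not enter the week-48 UMSARS comparison, and sham dose paths in the placebo arm give no ground for claiming a difference between arms. This is a minor correction, worth making because the wording bears on safety checks.

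**What to change.** - **4.1:** state that Visits 3–6, with the SoA panel and adverse-event review, occur for all participants in both arms whether or not the dose changes.
- **Timing:** where the dose was adjusted, draw the panel at the same visit as the level, 7 days (+3) after the adjustment. Fixing panels at Days 14, 21 and 28 while levels follow the adjustment date could split one visit into two draws for participants being escalated.
- **Content:** use the SoA panel, with no 24-hour urine at Visits 3–6, and remove it from 4.1 for those visits.
- **8.2 and schema:** add the first-month visits to 8.2, and bring the schema's Days 8, 15, 22 and Month 1 entries into line with the SoA.

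**Cost.** An edit to the text. In practice, participants whom 4.1 would have exempted have up to three first-month laboratory visits. These are already in the SoA and need not be at the centre: "SL: Safety labs visit, this can be done either at NYU or locally".

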Endpoints:	
Primary Endpoint: Change from baseline to 48 weeks (or last available date) in United Multiple System Atrophy Rating Score (UMSARS) total score compared with described progression rates in historical controls. We will assume that patients receiving sirolimus will have a change of 4 points less than those reported in natural history studies (see statistical section).
 
Secondary Endpoints:
 
 1. Change from baseline to 48 weeks (or last available date) in UMSARS-2 subscale score. We will assume that patients receiving sirolimus will have a change of 2 points less than those reported in historical controls. 2. Change from baseline to 48 weeks (or last available date) in UMSARS-1 subscale score. We will assume that patients receiving sirolimus will have a change of 2 points less than those reported in historical controls. 3. Magnetic resonance changes using dedicated algorithms to evaluate rate of change in diffusivity of defined areas of brain from baseline to 48 weeks. 4. Changes in retinal nerve fiber layer using optical coherence tomography from baseline to 48 weeks. 
Exploratory outcome
 
 1. Change in plasma biomarkers (exosomal alpha-synuclein particle concentration) from baseline to 48 months.

Study Population:	A total of 56 patients with multiple system atrophy will be randomized (42 to active agent and 14 to placebo)

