- CBC, CMP, CPK (8 ml of blood) and urinalysis with 24-hour urine collection
- Lipid panel (2 ml of blood)
- Sirolimus levels in blood (5 ml of blood)
- Adverse event reporting

In case the safety lab assessments are performed locally (e.g., at a local laboratory near the subjects' home), the PI or a licensed research member of the team will provide the patient with a prescription for the required tests. A research nurse, investigator or study manager will perform a phone call to assess adverse events within 7 days of the study visit.

To account for delays during the first month of treatment, Visit 7 (2-month) may be skipped to ensure that Visit 8 occurs 3 months (+/- 15 days) after the initiation of the study drug.

To maintain the blinding, the results of the sirolimus levels in blood will remain blinded to the investigators and study coordinators and delivered to the independent pharmacist in charge of determining if the sirolimus dosage should be increased or decreased.

End of study visit/early termination: the following tasks/procedures will be performed at the clinic during the termination visit (Study Visit 17):

- EKG
- MoCA
- Concomitant medications
- Physical examination
- Vitals signs
- CBC, CMP, CPK (8 ml of blood) and urinalysis with 24-hour urine collection
- Lipid panel (2 ml of blood)
- Sirolimus levels in blood (5 ml of blood)
- Retrieve study medication
- Recording of AE
- UMSARS scale
- Blood sample for exosomes (2 ml of blood)
- Retinal optical coherence tomography
- Brain MRI

We will accept a visit window of 15 days before or after the target date of this visit.

The reason for discontinuation of therapy will be documented in the source documents and captured on the CRF. In the event that the study drug is discontinued early, an early termination visit should be

completed as close to the last dose date as possible. Participants will be followed for the duration of 12 months.

If a participant is withdrawn because of an adverse event, the appropriate “Withdrawal Section” of the CRFs should be fully completed in addition to the Adverse Event module. The Independent Medical Monitor should be informed of all participants who are withdrawn for this reason. Participants will be followed for 12 months.

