7 STUDY INTERVENTION DISCONTINUATION AND PARTICIPANT DISCONTINUATION/WITHDRAWAL

7.1 DISCONTINUATION OF STUDY INTERVENTION

Discontinuation from study drug does not mean discontinuation from the study, and remaining study procedures should be completed as indicated by the study protocol. If a clinically significant finding is identified (including, but not limited to changes from baseline) after enrollment, the investigator or qualified designee will determine if any change in participant management is needed. Any new clinically relevant finding will be reported as an adverse event (AE).

The data to be collected at the time of study intervention discontinuation will include the following:

- EKG
- Concomitant medications
- Physical examination
- Vitals signs
- CBC, CMP, CPK, urinalysis
- 24-hour urine collection
- Lipid panel
- Sirolimus levels in blood
- Retrieve study medication
- Recording of AE
- UMSARS scale

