9 STATISTICAL CONSIDERATIONS

9.1 STATISTICAL HYPOTHESES

Primary Efficacy Endpoint: We hypothesize that treatment with sirolimus will show promise to slow the progression of the disease of patients with MSA. Specifically, our null hypothesis is that patients receiving sirolimus will have a UMSARS total score progression of only 4.6 points at week 48 higher than baseline, compared to a progression of 8.6 points at week 48 from baseline reported in historical controls from natural history studies and placebo-controlled trials of MSA. Our alternate hypothesis is that sirolimus will be futile to slow the progression of the disease in patients with MSA. The statistical definitions are as follows:

$H_0: \theta_E - \theta_p \leq 4$ where $\theta_p = 8.6$ points increase at week 48 from baseline described in historical controls
 $H_0: \theta_E \leq 4.6$ points increase at week 48 from baseline
 $H_1: \theta_E > 4.6$ points increase at week 48 from baseline

Secondary Efficacy Endpoints:

Brain MRI: We hypothesize that treatment with sirolimus will slow the increase of putaminal diffusivity in patients with MSA. Specifically, our null hypothesis states that patients receiving sirolimus will have a putaminal Trace (D) total score progression of 0.030×10^{-3} mm²/sec or less at week 48 versus baseline, compared to a progression of 0.070×10^{-3} mm²/sec at week 48 from baseline reported in specific longitudinal studies of MSA (41).

$H_0: \theta_E - \theta_p \leq 0.04$ where $\theta_p = 0.07$ ($\times 10^{-3}$ mm²/sec) increase in putaminal diffusivity at week 48 from baseline described in specific studies
 $H_0: \theta_E \leq 0.03$ points increase at week 48 from baseline
 $H_1: \theta_E > 0.03$ points increase at week 48 from baseline

Optical coherence tomography: We hypothesize that treatment with sirolimus will slow the thinning of the retinal nerve fiber layer (RNFL) in patients with MSA. Specifically, our null hypothesis states that patients receiving sirolimus will have a RNFL thickness thinning of 1.45 μ m at week 48 versus baseline, compared to a decrease of 3.7 μ m at week 48 from baseline reported in specific longitudinal studies of MSA (12).

$H_0: \theta_E - \theta_p \leq 2.25$ where $\theta_p = 3.7$ μ m decrease in RNFL at week 48 from baseline described in specific studies
 $H_0: \theta_E \leq 1.45$ μ m decrease at week 48 from baseline
 $H_1: \theta_E > 1.45$ μ m decrease at week 48 from baseline

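### Sections 4.1 and 7.1 contradict each other on MRI, OCT, exosome sample and MoCA at early drug stop, and the plan does not say whether week-48 imaging is then still due

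*Combined protocol and SAP*

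**What the plan says.** Section 4.1 has one heading for two situations, "End of study visit/early termination: the following tasks/procedures will be performed at the clinic during the termination visit (Study Visit 17"), followed by a single list. That list contains UMSARS, MoCA, the exosome blood sample, retinal OCT and brain MRI. On the timing of this visit after early drug stop it says: "completed as close to the last dose date as possible. Participants will be followed for the duration of 12 months".

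Section 7.1 introduces its own list with "The data to be collected at the time of study intervention discontinuation will include the following". The eleven bullets cover safety items, drug level, drug retrieval, adverse events and UMSARS. MRI, OCT, the exosome sample and MoCA are absent. The same section states: "Discontinuation from study drug does not mean discontinuation from the study, and remaining study procedures should be completed as indicated by the study protocol".

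The schedule of activities (1.3) has one follow-up MRI, one follow-up OCT and no early-termination column.

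The synopsis (1.1) defines the imaging endpoints as "Magnetic resonance changes using dedicated algorithms to evaluate rate of change in diffusivity of defined areas of brain from baseline to 48 weeks" and "Changes in retinal nerve fiber layer using optical coherence tomography from baseline to 48 weeks". For UMSARS, but not for imaging, it adds the last available date as an alternative to 48 weeks. Section 9.4.3 tests MRI and OCT in the sirolimus arm by one-sample t-tests against fixed values and handles missing data by multiple imputation.

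**The concern.** The site has two instructions for the same participant at the same moment. Under 4.1 it scans at drug stop and may record the visit as Study Visit 17. Under 7.1 it does not scan then, and the scheduled week-48 assessments remain to be done. Section 4.1 also times the closing phone call and the final safety assessment from the End of Study visit, so an early visit carrying the Visit 17 label can be read as starting the closing sequence.

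Two things are at stake. A week-48 scan that is not taken cannot be recovered. And the MRI and OCT comparators are fixed 48-week amounts of progression with no concurrent control in the test, so a scan taken after a shorter interval, if entered as week 48, shows less change because less time has passed.

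**Working it through.** **Step 1. The two sections side by side**

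| At early drug stop | Section 4.1 | Section 7.1 |
|---|---|---|
| Visit label | Shared heading with Study Visit 17 | None given |
| UMSARS | Listed | Listed |
| MRI, OCT, exosome sample, MoCA | Listed | Not listed |
| Afterwards | Followed for 12 months, content not stated | Remaining procedures to be completed |

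The lists conflict on four assessments. Neither section says whether a scan at drug stop replaces the week-48 scan or is additional to it. The schedule does not settle this.

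**Step 2. The plan's own bounds (9.1)**

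Bound = historical change minus assumed benefit.
- MRI: 0.07 - 0.04 = 0.03 (x10^-3 mm2/sec).
- OCT: 3.7 - 2.25 = 1.45 um, matching "RNFL thickness thinning of 1.45" um.

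Both are reproduced. The margins are therefore 0.04 and 2.25.

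**Step 3. Size of the lean if early scans were analysed as week 48**

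Assumptions: a drug with no effect; linear change over 48 weeks at the historical rate; a share f of the analysed arm scanned at a fraction t of 48 weeks, with that value used as week 48.

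Arm mean = historical value x [1 - f(1 - t)]

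Shift as a share of the margin = historical value x f(1 - t) / margin

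The plan gives no rate of early drug stopping. I use f = 10%, borrowing the dropout allowance in 9.2, as an assumption. Section 9.3 limits the analysis to those with at least 3 months of study drug, and 4.1 equates month 3 with day 84, so week 12 is about the earliest relevant stop.

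| Stop | MRI mean | Share of margin | OCT mean (um) | Share of margin |
|---|---|---|---|---|
| Week 12 (t = 0.25) | 0.0648 | 0.00525/0.04 = 13.1% | 3.42 | 0.2775/2.25 = 12.3% |
| Week 24 (t = 0.50) | 0.0665 | 0.0035/0.04 = 8.8% | 3.52 | 0.185/2.25 = 8.2% |
| Week 36 (t = 0.75) | 0.0683 | 0.00175/0.04 = 4.4% | 3.61 | 0.0925/2.25 = 4.1% |

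Range for a higher assumed stopping share, all at week 12:
- f = 20%: 0.0595 and 3.15 um (26% and 25% of the margins).
- f = 30%: 0.0543 and 2.87 um (39% and 37%).

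For the no-effect arm mean to reach the bound through week-12 scans alone, f would have to be 0.04/(0.07 x 0.75) = 76% for MRI and 2.25/(3.7 x 0.75) = 81% for OCT.

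**Step 4. Exosomes**

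Section 9.4.3 compares the sirolimus arm with placebo, and 9.1 expects a fall from baseline. A shorter interval could understate that fall, so no direction follows.

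**The case against.** The strongest reply is that the plan already contains the answer. Section 4.1 keeps early stoppers in follow-up for 12 months, and 7.1 separates stopping drug from leaving the study and wants the rest of the schedule done. An extra scan at drug stop, with week 48 still due, would fit both sections, since 7.1 says only what the data will include. MRI and OCT are defined at 48 weeks without the last-available-date alternative given for UMSARS, and Study Visit 17 has a target date with a 15-day window. On those definitions a week-12 scan is not the week-48 value, week 48 is missing, and imputation applies.

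Much of this stands. A reader might infer that 4.1 makes the drug-stop scan the final one, that week-48 imaging is then lost, and that imputation is bypassed. The documents do not say so. For a participant who leaves the study altogether, the drug-stop scan is the last one; for those who stay, the text is silent. Nor do they say that an early scan will be analysed as week 48, so the lean in step 3 is conditional.

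A reader might also infer a biased go/no-go decision. That is not supported: 9.4.2 rests futility on UMSARS total alone, and UMSARS is in both lists. Under 9.4.3 imaging is tested only after a significant primary result, which here means futility, and after the UMSARS sub-scores.

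What the reply does not remove is the conflict between the lists, the shared visit label, and the absence of any statement that week-48 imaging is still due or that an early scan is not the week-48 value.

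**Conclusion.** The contradiction between 4.1 and 7.1 is real and concerns when two secondary imaging endpoints are measured, so it should be reconciled. The consequence is limited and conditional. If an early scan were analysed as week 48, MRI and OCT would lean toward apparent benefit by about 4-13% of their margins. That figure rests on linear progression, no drug effect, and 10% of the analysed arm stopping between weeks 12 and 36; it grows in proportion to the stopping share, which the plan does not state. At this size the lean would not carry an ineffective drug to the bound. The exosome sample shares the contradiction over collection but not the direction of bias.

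**What to change.** - In 4.1, separate the two visits. Give early termination its own visit label and its own column in the schedule of activities, with the 7.1 list.
- Keep Study Visit 17, with UMSARS, MRI, OCT and exosome sample, at its week-48 target for every participant still in follow-up, on or off drug.
- Where a participant leaves the study and a scan is taken at exit, record it by its actual date, do not enter it as the week-48 value, and treat week-48 imaging as missing under 9.4.
- When adding the column, check that the schedule marks for follow-up MRI and OCT agree with 4.1, which places both at Study Visit 17.

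The cost is protocol and CRF wording and one schedule column. Participants still in follow-up have no more scans than the schedule already provides. The downside is that some early stoppers will not return at week 48, so their imaging values will be imputed.
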